## 8. STUDY POPULATION

This study will be conducted in approximately 81 female and male subjects, 2 to 17 years of age at the time of signing the initial informed consent, with a documented medical diagnosis of classic CAH due to 21-hydroxylase deficiency. Subjects must meet all inclusion criteria and no exclusion criteria to participate.

## 8.1. Subject Inclusion Criteria

To participate in this study, subjects must meet the following criteria:

- 1. Have documentation of witnessed written or oral pediatric assent from the subject deemed capable of providing assent, and written informed consent from the subject's parent(s) or legal guardian(s) (or the subject, if the subject has reached the age of majority) in accordance with the governing IRB/IEC and according to local laws and regulations.
- 2. Be a female or male 2 to 17 years of age with a body weight of at least 10 kg.
- 3. Have a medically confirmed diagnosis of classic CAH due to 21-hydroxylase deficiency based on standard medically accepted criteria such as elevated 17-OHP level, confirmed CYP21A2 genotype, diagnostic results after cosyntropin stimulation testing.
- 4. Be on a supraphysiologic glucocorticoid dose regimen defined as >12 mg/m²/day in hydrocortisone dose equivalents (see Section 9.3.2) that has been stable for at least 1 month prior to screening, is intended for chronic use, and consists ONLY of 1 or more of the following orally administered glucocorticoids: hydrocortisone, prednisone, prednisolone, or methylprednisolone. Subjects must be receiving a morning dose of glucocorticoid.
- 5. Have an A4 level (prior to the morning glucocorticoid dose) greater than the midpoint of the reference range, according to sex and either age (for Tanner stage 1) or pubertal stage (for Tanner stages 2 to 5).
- 6. Have a 17-OHP level (prior to the morning glucocorticoid dose) >2 × ULN according to sex and either age (for Tanner stage 1) or pubertal stage (for Tanner stages 2 to 5).
- 7. If treated with fludrocortisone, dose should be stable for at least 1 month prior to screening. Regardless of fludrocortisone treatment, upright plasma renin activity (PRA) (in the absence of medications that confound interpretation of PRA) during screening should be <3 × ULN and >lower limit of normal on the subject's usual sodium intake (if PRA >2 × ULN and <3 × ULN, subject must have normal age-specific systolic blood pressure and heart rate and serum potassium <ULN [Harman et al., 2011]).
- 8. Female subjects of childbearing potential with fertile male partners must either be completely abstinent from sexual intercourse (periodic abstinence is not acceptable) or agree to use contraception consistently from screening until the final study visit or 30 days after the last dose of study drug, whichever is longer. A subject of childbearing potential is defined as a female capable of becoming pregnant, which includes subjects who have had their first menstrual cycle (ie, menarche) and are not surgically sterile (ie,

bilateral oophorectomy, hysterectomy, or bilateral tubal ligation for at least 3 months prior to screening).

Acceptable methods of contraception are listed in Section 9.10.1.

## 8.2. Subject Exclusion Criteria

Subjects will be excluded from the study if they meet any of the following criteria:

- 1. Have a known or suspected diagnosis of any of the other forms of classic CAH including 11-β-hydroxylase deficiency, 17-α-hydroxylase deficiency, 3-β-hydroxysteroid dehydrogenase deficiency, P450 side-chain cleavage deficiency, or P450 oxidoreductase deficiency.
- 2. Have a history of bilateral adrenal ectomy, hypopituitarism, or other condition besides classic CAH due to 21-hydroxylase deficiency requiring chronic daily therapy with oral glucocorticoids.
- 3. Are at increased risk of developing adrenal crisis in the investigator's opinion, based on, for example, repeated history of adrenal crisis in the past, prior history of adrenal crisis precipitated by reducing glucocorticoid dose, recent episode(s), etc.
- 4. Have a clinically significant medical condition or chronic disease (including history of neurological, hepatic, renal, cardiovascular, gastrointestinal, significant malabsorption, hematologic, pulmonary, psychiatric, or endocrine disease [excluding CAH]) that in the opinion of the investigator would preclude the subject from participating in and completing the study or that could confound interpretation of study outcome.
- 5. Have a history of malignancy, unless successfully treated with curative intent and considered to be cured.
- 6. Have a known history of clinically concerning cardiac arrhythmia (including long QT syndrome) or prolongation of screening (pre-treatment) QT interval corrected for heart rate using Fridericia's correction (QTcF) of >450 msec (males) or >470 msec (females).
- 7. Have a known sensitivity (ie, hypersensitivity) or allergy to any corticotropin-releasing hormone receptor antagonist or any component of the study drug.
- 8. Have evidence of chronic renal or liver disease based on any of these screening laboratory test abnormalities:
  - Estimated glomerular filtration rate <60 mL/min/1.73 m^2.
  - Aspartate aminotransferase (AST) >2 × ULN.
  - Alanine aminotransferase (ALT) >2 × ULN.
  - Total bilirubin >1.5 × ULN unless due to a documented diagnosis of Gilbert's syndrome.
- 9. Have any of the following hematologic abnormalities at screening:
  - Hemoglobin <10 g/dL (age <6 years) or <11 g/dL (age  $\ge6 \text{ years}$ ).
  - White blood cell (WBC) count  $<4.0 \times 10^3/\text{mm}^3$ .
  - Platelet count <100,000/mm^3.

- Absolute neutrophil count  $<1.0 \times 10^3/\text{mm}^3$ .
- 10. Have any of the following coagulation abnormalities at screening:
  - Activated partial thromboplastin time (aPTT) that exceeds ULN values by more than 5 seconds.
  - Prothrombin time (PT) expressed as international normalized ratio (INR) >1.4, unless the subject is on anticoagulant treatment that affects INR.
- 11. Have serum sodium <130 mmol/L.
- 12. Used any active investigational drug within 30 days or 5 half-lives (whichever is longer) before screening, or plans to use an investigational drug (other than the study drug) during the study.
- 13. Are using any excluded concomitant medication (refer to Section 9.10) and cannot discontinue use of these medications for the duration of the study.
- 14. Have current substance dependence or substance or alcohol abuse (drugs including controlled substance or nonprescribed use of prescription drugs; nicotine and caffeine dependence are not exclusionary).
- 15. Have a significant risk of suicidal or violent behavior. Only for subjects ≥6 years of age: subjects with any suicidal ideation of type 4 (active suicidal ideation with some intent to act, without specific plan) or type 5 (active suicidal ideation with specific plan and intent) in the past 6 months before screening or lifetime history of suicidal behavior based on the C-SSRS should be excluded.
- 16. Have had a blood loss  $\ge 3\%$  of total blood volume (based on 75 mL per kg body weight) or donated blood or blood products within 8 weeks before Day 1 (baseline).
- 17. Females who are pregnant or lactating.
- 18. In the investigator's opinion, the subject is not capable of adhering to the protocol requirements (eg, ongoing and persistent noncompliance with glucocorticoid therapy).

## 8.3. Subject Identification and Replacement of Subjects

Subjects will be identified by their unique subject number. The subject number will be noted on electronic case report forms (eCRFs), all source documentation, laboratory documents, and ECG tracings. Subjects who discontinue from the study will not be replaced.

## 8.4. Randomization

Eligible subjects will be randomized 2:1 to either crinecerfont or placebo on Day 1 using an interactive response technology (IRT). Randomization will be stratified by pubertal stage (Tanner breast or genital stage 1 or 2 versus 3, 4 or 5) and sex (see Section 9.7.5.1 for further detail on Tanner staging).

## 9. STUDY EVALUATIONS

#### 9.1. Schedule of Assessments

A schedule of assessments for the screening period; the double-blind, placebo-controlled treatment period; and the open-label treatment period is shown in Table 7, and a schedule of assessments for the OLE is shown in Table 8.

Prior to any study-related procedures, parental or legal guardian (or subject, if the subject has reached the age of majority) informed consent with signed and witnessed study subject assent will be obtained (which may be done remotely, if allowed and remote consenting procedures are in place), as required by the governing IRB or ethics committee and according to local laws and regulations. At Week 52, the subject's parent(s) or legal guardian(s) (or the subject, if the subject has reached the age of majority) will review applicable portions of the ICF and the subject will review applicable portions of the assent form (if applicable) and confirm whether the subject will participate in the optional OLE for continued access to crinecerfont (Table 8). Subject-related events and activities including specific instructions, procedures, concomitant medications, dispensing of study drug, and descriptions of AEs should be recorded in the appropriate source documents and eCRFs.

All assessments during the core study as well as the OLE that are performed based on the subject's age should be based on the age at time of initial informed consent, unless otherwise specified.

Table 7: Schedule of Assessments – Double-Blind Placebo-Controlled and Open-Label Treatment Periods

Assessment	Screening Period a,b Double-Blind, Placebo-Controlle			led Treatr	ed Treatment Period a		Open-Label Treatment Period a			Follow-up Period for Subjects Not Entering the OLE a				
	Week -4 to Day -1	Day 1 (Baseline)	Week 4	Week 8	Week 12	Week 16	Week 20	Week 28	Week 32 b,d	Week 36 b,c	Week 4	Week 44b,	Week 52/ ET	Week 56°
Informed consent/assent	X	,												
Inclusion/exclusion criteria	X	Update												
Medical history	X	Update												
TSH and free T4	X (TSH only)	X						X					X	
UDS f	X													
Physical exam	X	X						X					X	
Tanner stage g	X	X				X		X			X		X	
Vital signs, height, weight h	X	X	X			X		X			X		X	X
Hematology/coagulation	X	X				X		X			X		X	X
Chemistry, cortisol	X	X		X	X	X		X	X	X	X		X	X
Urinalysis	X	X						X					X	X
CYP21A2 genotyping			X											
Pregnancy test i	X (s)	X (u)	X (u)			X (u)		X (u)			X (u)		X (u)	X (u)
Serial blood sampling (hormone) j		X	X											. ,
PK sample(s) incl serial k			X			X		X			X		X	
Salivary samples incl serial		X	X	X	X	X	X	X	X	X	X	X	X	
17-OHP, A4, ACTH m	X			X	X	X	X	X	X	X	X	X	X	X
Potential GC dose adjustment n			X	X	X	X	X		X	X	X	X		
LH, FSH, testosterone, PRA	X	X				X		X			X		X	
Fasting lipids, HOMA-IR		X						X					X	
Bone age n		X						X					X	
Testicular ultrasound o		X						X					X	
EQ-5D p		X						X					X	
PedsQL q		X						X					X	
PedsQL Family Impact		X						X					X	
BPRS-c r	X	X						X					X	
C-SSRS s	X	X	X			X		X			X		X	X
Hirsutism t and Acne Scales		X						X					X	
Menstrual Questionnaireu	X	X	X			X		X			X		X	X
Palatability/ease of admin v			X					X					X	
6- or 12-lead ECG	X	X	X					X					X	X
Dispense study drug		X	X			X		X			X			
Study drug accountability w			X			X		X			X		X	
AE monitoring	X	X	X	X	X	X	X	X	X	X	X	X	X	X
Prior & concomitant meds	X	X	X			X		X			X		X	X

OHP=17-hydroxyprogesterone; A4=androstenedione; ACTH= adrenocorticotropic hormone; admin=administration; AE=adverse event; BPRS-c=Brief Psychiatric Rating Scale, Children's Version; C-SSRS=Columbia-Suicide Severity Rating Scale; CYP=cytochrome P450; ECG=electrocardiogram; ET=early termination; FSH=follicle-stimulating hormone; GC=glucocorticoid; HOMA-IR=homeostatic model assessment of insulin resistance; incl=including; LH=luteinizing hormone; OLE=open-label extension; PedsQL=Pediatric Quality of Life Instrument; PK=pharmacokinetics; PRA=plasma renin activity; s=serum; T4=thyroxine; TSH=thyroid-stimulating hormone; u=urine; UDS=urine drug screen.

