- Day 1 and Weeks 4, 28, and 52/ET: at approximately 0600 hours, at approximately 0800 hours prior to dosing with morning GC and (after Day 1) study drug and at approximately 3 and 6 hours after dosing, and within 30 minutes prior to the evening dose of GC; if subject is not on an evening GC dose, then prior to bedtime. Any midday GC dose that the subject is receiving should be taken after the salivary sample collection 6 hours after dosing.
- Weeks 8, 12, 16, 20, 32, 36, 40, 44, and 56: prior to morning GC dose at approximately the same time as the blood sample. If a blood sample is not obtained at a visit (eg, because no GC dose adjustment was required), a salivary sample does not need to be obtained.
- m Subjects should take their GC dose the night before prior to 2100 hours and hold their morning dose of GC, fludrocortisone (if applicable), and study drug (except screening) until after predose blood sample collection. The blood sample collection will include 17-OHP and A4 at all visits, and will also include ACTH at Weeks 16, 28, 40, 52/ET, and 56. Morning dosing should occur between approximately 0800 and 0830 hours with breakfast. At Week 28 and Week 52/ET, another blood sample will be collected at 3 hours after dosing for subjects ≥6 years of age with body weight ≥20 kg.
- n Only in females with the most recent prior bone age <14 years and males with the most recent prior bone age <16 years. Bone age assessment is not required at the ET visit if the subject had a bone age assessment within 3 months prior.
- Only in male subjects. Week 28 and Week 52/ET ultrasound only if testicular adrenal rest tumor(s) demonstrated on Day 1. Testicular ultrasound is not required at the ET visit if the subject had a testicular ultrasound within 3 months prior.
- p EQ-5D-Y for age 8 to 15 years, EQ-5D-5L for age 16 years and older.
- q PedsOL Toddler Version for age 2 to 4 years, Young Child Version for age 5 to 7 years, Child Version for age 8 to 12 years, Adolescent Version for age 13 to 17 years.
- r Only for subjects ≥3 years of age.
- S Only for subjects >6 years of age. Baseline/Screening version used at screening, and Since Last Visit version at subsequent visits.
- t Hirsutism scale only for females.
- u Menstrual Cycle Ouestionnaire only for females who have undergone menarche and are not on hormonal or intrauterine device contraceptives.

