- At these visits, subjects should take their GC dose the night before prior to 2100 hours and hold their morning dose of GC, fludrocortisone (if applicable), and study drug until after predose blood sample collection. Dosing with the morning GC, fludrocortisone (if applicable), and study drug should occur between approximately 0800 and 0830 hours with breakfast. At Month 24 and every 12 months thereafter, and at ET, another blood sample will be collected at 3 hours after dosing for subjects >6 years of age with body weight >20 kg.
- m Only in females with the most recent prior bone age <14 years and males with the most recent prior bone age <16 years. Bone age assessment is not required at the early termination visit if the subject had a bone age assessment within 3 months prior.
- n All male subjects continuing in the OLE will have a testicular ultrasound at Week 52, including subjects who are not required to have a Week 52 ultrasound as part of the core study. An ultrasound will be performed at Month 24 and every 12 months thereafter only if the Week 52 ultrasound demonstrates the presence of TARTs. All male subjects will have a testicular ultrasound at the early termination visit except for subjects who have had a testicular ultrasound within 3 months prior to the early termination visit.
- ° EQ-5D-Y for age 8 to 15 years, EQ-5D-5L for age ≥16 years. Subjects entering the OLE will have age recalculated and use the appropriate EQ-5D instrument based on age of entry into the OLE.
- P Only for subjects ≥3 years of age. In the OLE, the BPRS-c will continue to be administered to subjects who are ≥18 years of age.
- q Only for subjects ≥6 years of age.
- r Hirsutism scale only for females.
- Menstrual Cycle Questionnaire only for females who have undergone menarche and are not on hormonal or intrauterine device contraceptives.
- t Study drug will be dispensed every 3 months.
- u Subjects will return all unused study drug, and a compliance check will be performed by counting the capsules returned, at each study visit except for the additional visits that occur 1 month after doubling of the evening dose for inadequate efficacy.

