## 9.4. Patient and Caregiver Reported Outcomes

## 9.4.1. EQ-5D

The EQ-5D-Y will be administered to subjects 8 to 15 years of age. This instrument has children self-report on 5 dimensions of health: Mobility, Looking After Myself, Usual Activities, Pain/Discomfort, and being Worried, Sad, or Unhappy. Each dimension has 3 levels of severity: "no problems", "some problems", or "a lot of problems" (Scott et al., 2017). The subject indicates his/her health state by checking the box next to the most appropriate statement. Subjects also rate their overall health on a 0 to 100 hash-marked, vertical visual analogue scale, where 100 is labeled "The best health you can imagine" and 0 is labeled "The worst health you can imagine." This instrument has been validated in international population samples of children and adolescents (Ravens-Sieberer et al., 2010).

The EQ-5D-5L will be administered to subjects ≥16 years of age. This instrument is a general, single index measure for describing and valuing health (Herdman et al., 2011). It defines health in terms of 5 dimensions: Mobility, Self-Care, Usual Activities, Pain/Discomfort, and

Anxiety/Depression. Each dimension has 5 levels: no problems, slight problems, moderate problems, severe problems, and extreme problems. The subject indicates his/her health state by checking the box next to the most appropriate statement. The scores for the 5 dimensions can be combined into a 5-digit number that describes the subject's health state. Subjects also rate their overall health on a 0 to 100 hash-marked, vertical visual analogue scale, where 100 is labeled "The best health you can imagine" and 0 is labeled "The worst health you can imagine."

The version of EQ-5D used in the OLE should be based on the subject's age at Month 12/Week 52.

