#### 9.7.8. Columbia-Suicide Severity Rating Scale

The C-SSRS is a validated instrument to prospectively assess suicidal ideation and behavior (http://www.cssrs.columbia.edu) and will be used only for subjects ≥6 years of age. There are versions of the questionnaire designed for use at screening (baseline/screening version) and at baseline and visits throughout the study (Since Last Visit version). All versions of the C-SSRS include a series of screening questions related to suicidal ideation and suicidal behavior. Subject responses of "yes" to one or more screening questions will prompt additional questions that evaluate frequency and intensity of suicidal ideation and/or behavior. Subjects with any suicidal ideation of type 4 (active suicidal ideation with some intent to act, without specific plan) or type 5 (active suicidal ideation with specific plan and intent) in the past 6 months before screening or lifetime history of suicidal behavior based on the C-SSRS should be excluded from participation in the study (see exclusion criterion #15).

The C-SSRS will be administered and scored by the investigator or qualified study center personnel as specified in Table 7 and Table 8.

Appropriate psychiatric evaluation and intervention will be provided for any treatment-emergent suicidal behavior or clinically significant suicidal ideation.

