- Collect salivary samples for hormone assessment at approximately 0600 hours, at approximately 0800 hours prior to morning glucocorticoid dosing and 3 and 6 hours after dosing, and within 30 minutes prior to the evening dose of glucocorticoid; if subject is not on an evening glucocorticoid dose, then prior to bedtime.
- Perform x-ray to assess bone age (only in females with the most recent bone age <14 years and in males with the most recent bone age <16 years; see Section 9.3.4).
- Perform testicular ultrasound (males only).
- Administer the EQ-5D (EQ-5D-Y for age 8 to 15 years, EQ-5D-5L for age 16 to 17 years); the PedsQL (PedsQL Toddler Version for age 2 to 4 years, Young Child Version for age 5 to 7 years, Child Version for age 8 to 12 years, Adolescent Version for age 13 to 17 years); and the PedsQL Family Impact.
- Administer the BPRS-c (only for subjects ≥3 years); and the C-SSRS (Since Last Visit version; only for subjects ≥6 years).
- Administer the Hirsutism (female subjects only) and Acne Scales.
- Review the Menstrual Cycle Questionnaire (only females who have undergone menarche and are not on hormonal or intrauterine device contraceptives).
- Perform 6- or 12-lead ECG.
- Dispense study drug: first dose to be taken at home with the subject's evening meal; thereafter, study drug will be administered bid with the subject's breakfast and evening meal (each dose separated by approximately 12 hours).
- Record concomitant medications.
- AE monitoring.

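### Read literally, the consent-age rule leaves a child under 6 at consent with no scheduled C-SSRS after turning 6; basing eligibility on age at each visit is a low-priority, cheap improvement

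*Protocol*

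**What the plan says.** The default is stated twice, in the Synopsis (Study Assessments and Study Visit Scheduling) and in Protocol 9.1. Assessments that depend on age, in the core study and in the OLE, "should be based on the age at time of initial informed consent, unless otherwise specified".

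Protocol 9.7.8 says that the C-SSRS "will be used only for subjects ≥6 years of age". The footnotes of Tables 7 and 8, the visit lists in 9.8 and SAP 11.6 give the same threshold of 6 years. None of them says at what date the age is taken. On versions, Table 7 says: "Baseline/Screening version used at screening, and Since Last Visit version at subsequent visits".

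Two other instruments do carry an age provision for the OLE. For the EQ-5D, Table 8 says: "Subjects entering the OLE will have age recalculated and use the appropriate EQ-5D instrument based on age of entry into the OLE", and 9.4.1 agrees: "The version of EQ-5D used in the OLE should be based on the subject's age at Month 12/Week 52". For the BPRS-c, Table 8 says: "In the OLE, the BPRS-c will continue to be administered to subjects who are ≥18 years of age".

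Protocol 9.11.1 requires study drug to be stopped for suicidal behavior, or for ideation of type 4 or 5 as graded on the C-SSRS.

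**The concern.** Eligibility starts at age 2, and the OLE is expected to average about 24 months, so some children may pass their sixth birthday on drug. The protocol treats the C-SSRS as a safety tool from age 6 and ties a mandatory stop to its grading. Under the literal rule, a child who reaches 6 on study is screened less than a child of the same age who was already 6 at consent, and the protocol gives no reason for the difference.

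The second problem is consistency. If some sites apply consent age and others current age, C-SSRS data from children of the same age will not be comparable. What is at stake is safety monitoring and the descriptive C-SSRS tables. The primary and key secondary endpoints do not depend on this scale.

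**Working it through.** The plan gives no figure to reproduce. The check is a reading of the text, followed by a rough sizing.

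**Reading**

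1. The default is age at consent, and it expressly covers the OLE, so age stays fixed beyond Week 52 unless a specific text says otherwise.
2. Such a text exists for the EQ-5D, whose age is recalculated at OLE entry. None exists for the C-SSRS in 9.7.8, Tables 7 and 8, the visit lists, SAP 4.6 or SAP 11.6.
3. The default therefore governs, and a child under 6 at consent is outside the C-SSRS schedule throughout.
4. The BPRS-c note points the other way. Nobody can be 18 or over at consent (range 2 to 17), so that note must refer to current age. It shows that a site could reasonably read the C-SSRS threshold as current age too.

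**How many children**

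The documents give no age mix and no quota for children under 6; 8.4 stratifies by pubertal stage and sex only. The minimum is 0. The figures below rest on an assumption: an even spread over the 16 age-years from 2 to 17, which gives 81 / 16 = 5.06 children per age-year. Screening lasts 4 weeks, or 8 with the permitted extension. Expected number turning 6 = (weeks from consent / 52.18) × 5.06.

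| Consent at | By | Weeks | Years | Even spread | Twice the density |
|---|---|---|---|---|---|
| Week -4 | Week 28 | 32 | 0.613 | 3.1 | 6.2 |
| Week -8 | Week 28 | 36 | 0.690 | 3.5 | 7.0 |
| Week -4 | Week 52 | 56 | 1.073 | 5.4 | 10.9 |
| Week -8 | Week 52 | 60 | 1.150 | 5.8 | 11.6 |

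These counts include children who turn 6 between consent and Day 1. On the even spread that is 4 / 52.18 × 5.06 = 0.4 of a child, or 0.8 with 8 weeks. The OLE adds further children, with no firm ceiling because it has no fixed end.

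**How many visits**

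After Week 4, Table 7 schedules the C-SSRS at Weeks 16, 28, 40 and 52, and Table 8 at Month 18 and every 6 months after. The BPRS-c falls at Weeks 28 and 52, then Month 24 and every 12 months. With consent at Week -4 and follow-up to Month 36:

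| Age at consent | Turns 6 at | C-SSRS visits missed | BPRS-c visits held |
|---|---|---|---|
| 5 y 10 m | Week 4.7 | 8 (Weeks 16, 28, 40, 52; Months 18, 24, 30, 36) | 4 |
| 5 y 0 m | Week 48.2 | 5 (Week 52; Months 18, 24, 30, 36) | 3 |
| 4 y 0 m | Week 100.4 | 3 (Months 24, 30, 36) | 2 |

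Reaching Month 36 supposes about 24 months in the optional OLE.

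**The case against.** The best case for the plan has four parts.

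- The rule is deliberate. It is stated twice, covers the OLE by name, and keeps each child on one set of assessments. That stands as a reason to keep it for other items such as serial sampling, but it does not explain why suicidality screening should follow age at consent.
- The literal reading is not the only one. This stands: the BPRS-c note supports current age. It argues for a clarifying sentence rather than for silence.
- The protection that remains is real. Suicidal behavior triggers the stop without any scale (9.11.1). Suicidal behavior and clinically significant ideation are recorded as AEs at any age (11.1). Section 9.7.8 adds: "Appropriate psychiatric evaluation and intervention will be provided for any treatment-emergent suicidal behavior or clinically significant suicidal ideation". An AE or the investigator's decision can end dosing, the BPRS-c is given from age 3, and nothing bars an unscheduled C-SSRS. All of this stands. It falls short of scheduled graded screening, because 11.1 asks for general questioning without prompting for particular symptoms and the BPRS-c is less frequent.
- The protocol reports no signal. In the adult depression study in 5.2, any suicidal ideation on the C-SSRS was 18.0% to 26.5% across crinecerfont doses against 18.4% on placebo. Those were adults, but nothing in the documents raises the priority.

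A reader might infer that these children go unmonitored for suicidality, or that the mandatory stop cannot operate for them. The documents do not support either. Only the type 4/5 ideation limb lacks a scheduled instrument, and only under the literal reading.

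**Conclusion.** The gap exists on a literal reading: the consent-age default applies, no C-SSRS text overrides it, and one limb of a mandatory stop then has no scheduled instrument for a child who was under 6 at consent. How sites would read the rule in practice cannot be settled from the documents.

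Its size is small and uncertain. The number of children may be zero. About 3 by Week 28 and 5 to 6 by Week 52 depend wholly on the assumed even age spread, and doubling the density around age 5 gives 6 to 7 and 11 to 12. Safety data are summarized descriptively without hypothesis tests (SAP 11), and no efficacy endpoint is involved. This is a low-priority, cheap improvement to safety monitoring, held with medium confidence.

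**What to change.** At the next amendment, state in the Synopsis, 9.1, 9.7.8 and the C-SSRS footnotes of Tables 7 and 8 that C-SSRS eligibility is based on age at each visit, with two cases:

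- **Turns 6 after consent, on or before Day 1.** Give the Baseline/Screening version before randomization and apply exclusion criterion 15. The child then has a baseline score.
- **Turns 6 after Day 1.** Give the Since Last Visit version from the first scheduled C-SSRS visit at or after age 6. Recall reaches back no further than the Day 1 visit, after which comes the "first dose to be taken at home with the subject's evening meal", so it covers essentially on-treatment time. It counts as a postbaseline assessment. The child stays out of the double-blind shift table, because SAP 11.6 already omits subjects without a baseline score.

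The Baseline/Screening version should not be the routine first assessment after Day 1. With the look-back periods in SAP 11.6 (6 months for ideation, 1 year for behavior), giving it at Week 16 would reach to about Week 16 - 26 = -10 and Week 16 - 52 = -36. Pre-dose events would then enter the postbaseline summary. If a lifetime history is also taken, list it separately from that summary. Any type 4/5 ideation or suicidal behavior that it shows after the first dose must still trigger the stop in 9.11.1, which makes no exemption.

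The consent-age rule stays for other assessments. The cost is wording in five places, a clause in the Day 1 visit list for the first case, and a clarifying sentence in SAP 11.6 and the separate OLE SAP. The nine later visit lists that name the Since Last Visit version can stay as they are. Protocol 14.3 requires a formal amendment, at approximately 40 centers, so this should travel with the next one. The burden is a short questionnaire for a few children at visits already scheduled.
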